4.1.3 Other study parameters (if applicable)

Baseline parameters include: sex, age, body weight, type of disorder, socio-economic status, comorbidities and medication use.

4.2 Study procedures

Participants will accomplish the Experience Sampling Method for seven consecutive days during their regular daily life. Previous ESM validation studies validated for the use of the ESM for seven days too.⁴³

During the last three consecutive days of the ESM, patients will also keep a SR-BD following the standard of care. A 7-day voiding diary is a reliable and valid method for documenting the change in symptoms of overactive bladder in men and women with predominantly urge incontinence. However, 3-day voiding diaries are as accurate as the 7-day diary, but patient burden is reduced. Therefore, a 3-day sensation-related bladder diary is used in the standard of care of the department of Urology of MUMC+, Zuyderland Heerlen/Sittard and University Hospital Antwerp.^{46,47} Furthermore, during the first four days of the study, ESM outcomes are not influenced by outcomes reported with the sensation-related bladder diaries. This is in alignment with previous studies.^{4,43}

On the last day of the study period, participants will fill out the several retrospective symptom questionnaires.

To accomplish the ESM, they need to carry their own smartphone or (in case they do not have one) another digital device, which will be lent to them for this period. On the smartphone or digital device an application, specifically developed for this project, will be downloaded. This application will run the PROM as follows.

The concerning device will send out an auditory signal 10 times a day at random moments between 07:00 am and 22:00 pm. During 10 minutes following the signal participants can complete a questionnaire, *i.e.* the developed PROM, on the device (see F1. 'ESM_Vragenlijst_Versie 1.0 (11.08.2017)'). After these 10 minutes the questionnaire will not be available until the next beep and is considered missing data. Therefore, subjects are instructed to complete as many questionnaires as possible each day, as soon as possible following each beep, but to pass over questionnaires when completing is impossible. For example, subjects should not fill out questions when driving a car. The questions will be identical between the different moments during the day.

Additionally, participants will be instructed to complete a different ESM questionnaire in the morning when they wake up (see F1. 'ESM_Ochtend Vragenlijst_Versie 1.0 (11.08.2017)'). A timeline portraying which questionnaire has to be filled out at what time during the study period is reported in figure 2.

4.2.1 **PROM** development

The process of question selection for the development of an OAB specific ESM tool is a crucial step since content, construct and criterion validity are dependent on these questions. The questions that will be used were derived from previously published ESM studies and currently used OAB symptom questionnaires and further selection took place based on patients input during focus group interviews. Following, the items were evaluated by a multidisciplinary expert group consisting of highly esteemed and experienced investigators in the fields of urology, gastroenterology, psychiatry and gynaecology. Herewith, the number of items was further reduced in order to minimize the burden associated with completing the questionnaire at regular intervals.

This stepwise approach was performed according to guidelines for symptom assessment tool development.

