Main study endpoints: The main study outcome comprehends the psychometric properties of the PROM for symptom assessment of OAB symptoms. Secondary outcomes are increase in ESM score for OAB symptoms and environmental and psychosocial factors (*e.g.* as measured by the PROM) from one time point (t-1) to the next (t).

Burden, risks and benefits: The burden that is associated with participation in this study comprises completing the PROM questionnaire several times a day, which interrupts daily life due to its random character. Furthermore, the burden is limited to completing a SR-BD and other symptom questionnaires. Most importantly, participating does not bring along

important health related risks. However, awareness could trigger symptoms and therefore be considered as a burden. Nevertheless, for the patients it could be beneficial too to know what triggers complaints, to cope better with their disease.

INTRODUCTION AND RATIONALE

The overactive bladder syndrome (OAB) is defined by the International Continence Society (ICS) as a symptom complex of urgency, usually with frequency and nocturia (awakening at night to void), with (OAB wet) or without (OAB dry) urinary urgency incontinence. Urgency is the complaint of a sudden compelling desire to pass urine, which is difficult to defer⁵. OAB is clinically diagnosed using the ICS criteria of \geq 8 micturitions and at least 1 urgency episode per 24 hours.

It is estimated that approximately 16-17% of the adult population of the Western world is affected by OAB ^{6,7}. The incidence of OAB, both wet and dry increases by age ⁸⁻¹⁰, and because of the worldwide ageing of the population, the number of adults affected by urinary urgency incontinence (UUI) would increase ¹¹. The health care costs of OAB are high ¹², and work productivity can be significantly impacted as well ¹³. In addition, OAB can be associated with comorbidity and increased mortality^{14,15}. Furthermore, OAB with and without incontinence has been associated with significantly lower quality of life scores compared to matched controls without voiding complaints⁸. It is of particular interest that OAB does not only affect the patients, but also has an impact on family members ¹⁰.

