4.2.2 Tool development

To apply ESM as a symptom assessment method in this study, an application suitable for smartphones has been developed. This application runs the previously selected set of items, as described in section 5.2.1.1. 'PROM development'.

The application can be downloaded freely on the personal smartphone of each participating subject. Once the application is downloaded and activated, it will work both online and offline to ensure that no assessments will be missed when not connected to the Internet. In online situations the answers will be directly and automatically sent to the general database; when offline the answers will be temporary stored at the smartphone and will be sent to the database as soon as an Internet connection is available. Encryption of data to assure on patient's privacy is described in detail in section 9.1 'Handling and storage of data and documents'.

Questions in the application will be designed in a hierarchical order, *i.e.* if the patient has no symptoms at that particular moment, there is no rationale for assessing triggers and therefore these questions will be automatically set to a default of "no" or "none". Further, if patients find an auditory signal

disturbing during their daily activities, they will be able to choose a vibration signal instead.

- 4.2.3 Retrospective symptom assessment conventional questionnaires Apart from ESM, participants will be instructed to complete a SR-BD during last 3 consecutive days of filling out the ESM (see 'F2. ESM_sensationrelated bladder diary_Versie 1.0 (11.08.2017)'). The SR-BD has to be filled out after each micturition. This is a voiding diary where people fill out at what time they had to void, how high the voided volume was and how high the urgency and perception of bladder fullness was what they experienced. Furthermore they have to fill out if and how much urine loss they had. Furthermore, participants will be instructed to complete additional (singletime) retrospective questionnaires, at the end of the test period of 7 days:
 - Baseline questionnaire for demographic characteristics (see F1.
 'ESM_Algemene Vragenlijst_Versie 1.0 (11.08.2017)').

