6. STATISTICAL ANALYSIS

Part I – Comparison of the ESM to SR-BDs and other retrospective questionnaires

In case of incomplete ESM data, we will not use imputation techniques as these techniques have similar assumptions on the mechanisms of missing data as the statistical model described in the remaining text.

Experience Sampling Methods produce complex multilevel data structures, and analysis techniques need to take the variation between subjects and repeated measures within subjects into account. Associations between urological symptom scores of the SR-BD and corresponding ESM scores will be tested using linear mixed-effects models, with a random intercept to account for clustering of measurements within patients, and an autoregressive (AR1) covariate structure to account for correlations of measurements over time. Currently the SR-BD can be seen as the standard method and will therefore be used as dependent variable in the analysis. For each participant, ESM day-mean scores of individual symptoms will be used as predictor, to test whether average symptom scores of the day reflect the day-mean SR-BD scores.

To quantify the difference of scores between the two methods, ESM data will be subtracted from corresponding day-mean SR-BD scores, resulting in a delta score, which will be statistically tested using the same multilevel analysis, adjusting for repeated measures. In like manner, the differences between the mean SR-BD scores and ESM maximum scores of the day will be tested.

To investigate if certain patient characteristics lead to a different retrospective perception of urgency, possible predictors of a larger delta-score (i.e. the differences in urgency reporting between ESM day-mean scores and the day-mean SR-BD scores) will be tested: i.e. gender, age, presence of comorbid panic disorder and psychological symptoms (HADS).

Part II Validation

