6.1 Primary study parameter

Data used for analysis will comprise patient-reported scores from ESM, paper SR-BDs and single-time paper symptom questionnaires. The PROM will be psychometrically evaluated with regard to validity and reliability. These parameters will characterize the ESM measure and allow insight into the potential role of this method in clinical practice. Validity and reliability will be assessed according to following components ^{29,62,63}:

- Content validity reflects the extent to which the instrument as a whole measures all the relevant aspects that are indicative to the specific condition and population. This can be determined by taking into account evidence from qualitative studies, performing cognitive interviews to evaluate patients' understanding with the instrument and by taking into account experts' opinions ^{62,63}. In this study, content validity is assured by basing ESM items on theoretical constructs from the literature as well as by performing patient focus groups and expert meetings.
- Concurrent validity reflects the correlation between a new test and an existing test that purport to measure the same construct. ESM scores will be correlated with scores of so-called 'concurrent' instruments. In the present study, ESM measures will be compared to scores obtained from SR-BDs and symptom questionnaires. Since ESM data have a hierarchical structure, with repeated measurements (level 1) nested within subjects (level 2), these analyses will be performed using linear mixed-effects models, including a random intercept and an autoregressive (AR1) covariate structure. ^{62,63}.
- To quantify the difference of scores between the two methods (ESM and SR-BD), a delta score is calculated. Using the same multilevel analysis, thus adjusting for clustering within patients and for correlations between repeated

measures, we will test whether this delta score is different from 0. In like manner, the differences between SR-BD scores and ESM maximum scores of the day will be tested.

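### The diary day-mean includes voids between 22:00 and 07:00 that no ESM beep can match, so the SR-BD minus ESM delta carries a time-window component of unknown sign

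*Combined protocol and SAP*

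**What the plan says.** Section 4.2 sets the momentary side of the comparison: "The concerning device will send out an auditory signal 10 times a day at random moments between 07:00 am and 22:00 pm". It adds that "participants will be instructed to complete a different ESM questionnaire in the morning when they wake up". The content of that waking form is in an attachment not included in the document, and sections 6 to 6.2 give it no role in any ESM score.

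Section 4.2.3 sets the diary side: "The SR-BD has to be filled out after each micturition". It continues: "This is a voiding diary where people fill out at what time they had to void". Urgency is among the items scored at each void. No hours are excluded. The Summary also presents the diary as a means of checking criteria counted per 24 hours, which a daytime-only diary could not do. The Introduction defines OAB "as a symptom complex of urgency, usually with frequency and nocturia (awakening at night to void".

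Section 6, Part I, joins the two sides: "ESM data will be subtracted from corresponding day-mean SR-BD scores, resulting in a delta score". Section 6.1 adds that "we will test whether this delta score is different from 0". The same sections compare the diary with the ESM maximum of the day. Section 6 also uses the ESM day-mean to predict the diary day-mean, and sections 6 and 6.2 look for patient characteristics that predict a larger delta. Neither *day* nor *corresponding* is defined, and no rule matches diary voids to the beep window. Section 1, Part I, expects mean urgency to be significantly lower on ESM than on the diary.

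**The concern.** Following the plan as written, the two day-means average over different parts of the same day. The beeps cover 15 hours. The diary covers all 24, including night voids, voids after 22:00 before bed and voids before 07:00 on rising. This would remain even if patients rated urgency identically on both instruments during the day.

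The delta is meant to measure how the two methods differ. If urgency at out-of-window voids differs from urgency at in-window voids, part of the delta is a difference between times of day. The other analyses are affected in related ways:

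- **Day-maximum:** an urgency peak outside the beep window cannot appear in the ESM maximum.
- **Association:** diary entries from hours that ESM does not sample can weaken the association between the day-means, and section 1 judges agreement against correlation bands of 0.4 to 0.8.
- **Predictors of delta:** a characteristic that goes with the number or urgency of out-of-window voids could look like a predictor of retrospective perception.

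**Working it through.** **The plan's own figure.** There is no power calculation or expected size for delta. The only sample-size arithmetic, in section 3.4, inflates 50 usable patients for non-valid data: 50/(1 - 0.23) = 64.9, or 50/(1 - 0.232) = 65.1, consistent with the stated 66. It does not bear on this point, except that n = 50 is used below.

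**Length of the uncovered period.** 22:00 to 07:00 is 9 hours, and 9/24 = 37.5%. This is a share of hours, not of voids.

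**Shift in delta.** Let f be the share of a day's diary voids outside the window, U_in and U_out the mean diary urgency inside and outside it, and E the ESM day-mean.

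- Diary day-mean = (1 - f) × U_in + f × U_out = U_in + f × (U_out - U_in)
- Delta = (U_in - E) + f × (U_out - U_in)

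The second term is the window component. It is present even when U_in = E.

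**Assumed inputs.** The documents give no void counts by time of day and no urgency by time of day. They state an 11-point scale for ESM (section 6.1) but no scale for diary urgency. Assumed: 1 to 3 of 8 to 12 voids out of window, a difference of -2 to +2 points, and an 11-point diary scale.

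- Smallest share: 1/12 = 0.083. Shift for ±1 point: ±0.08; for ±2 points: ±0.17.
- Largest share: 3/8 = 0.375. Shift for ±1 point: ±0.375; for ±2 points: ±0.75.
- Equal urgency: shift 0 at any share.

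The range is about -0.75 to +0.75. Its ends pair the most out-of-window voids with the fewest total voids and the largest difference.

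**Effect on the test of delta against 0.** This illustration uses n = 50, one value per patient (ignoring the three repeated diary days), a normal approximation and two-sided alpha 0.05. The SD of delta is assumed to be 1, 1.5 or 2. The smallest significant mean delta is 1.96 × SD/√50 = 0.28, 0.42 or 0.55. If the methods agree perfectly inside the window, the chance of a significant delta is:

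| Out-of-window voids | Urgency difference | Shift | SD 1 | SD 1.5 | SD 2 |
|---|---|---|---|---|---|
| any | 0 | 0 | 5% | 5% | 5% |
| 1 in 10 | ±1 | ±0.10 | 11% | 8% | 6% |
| 1 in 10 | ±2 | ±0.20 | 29% | 16% | 11% |
| 2 in 10 | ±1 | ±0.20 | 29% | 16% | 11% |
| 2 in 10 | ±2 | ±0.40 | 81% | 47% | 29% |
| 3 in 11 | ±2 | ±0.55 | 97% | 73% | 49% |

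The significant result points towards lower ESM scores when the difference is positive and towards higher ESM scores when it is negative.

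**After matching the windows.** With only in-window voids, f = 0 and the second term vanishes by construction. The first term is unchanged.

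**The case against.** The strongest reply concerns direction. A reader might infer that the mismatch pushes delta towards the hypothesis, or could produce the hypothesised result unaided. The documents do not support that. Nocturia means more night voids, not more urgent ones, and daytime voids in OAB also follow an urge. Some out-of-window voids occur while the patient is awake, before bed or on rising. One out-of-window void in 10 with a 1-point difference moves delta by only 0.1. A reader might likewise infer that age, a planned predictor, would stand in for nocturia. The Introduction says OAB becomes more frequent with age but links neither night voiding nor its urgency to age among these patients. These objections stand.

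A second reply is that the waking questionnaire may cover the night. Its content is not available, so this cannot be excluded, but the analysis sections do not bring it into the ESM score.

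A third is that section 6 treats the diary as the standard method, so setting ESM against the full diary is a legitimate question, and dropping night voids could flatter ESM. This has force. It is why the 24-hour comparison should be kept and reported. It does not justify leaving the window difference inside a delta read as a difference between methods.

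The last is that a probably larger difference is left untouched: the diary scores urgency at a void, ESM at a random moment. For illustration, if urgency rises linearly from 0 to 6 between voids, the time average is 3 and the void score 6, a delta of 3 with no night voids at all. Section 1 partly anticipates this by expecting the diary to reflect the daily peak. That stands as a limitation. It does not remove the window problem, which the plan does not acknowledge.

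**Conclusion.** The point holds as a mismatch of time windows. The plan puts out-of-window voids on one side only of a delta tested against 0, with no matching rule and no sensitivity analysis. That voids are recorded at all hours is inferred from the instruction to score each one and from the diary's use for 24-hour criteria.

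The sign of the shift is unknown: towards the hypothesis if out-of-window urgency is higher, zero if equal, against it if lower. Its size, about -0.75 to +0.75 points, rests wholly on assumed void counts, urgency differences and diary scale, and many plausible combinations give far less. No bias in a given direction is shown. What is shown is that a non-zero delta could not be attributed to the method alone, and that one of the competing explanations can be removed with data already collected. It is worth correcting before analysis.

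**What to change.** In section 6, Part I, and section 6.1:

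- Define *day* and *corresponding*. For the association, delta, day-maximum and delta-predictor analyses, compute the SR-BD day-mean from voids timed 07:00 to 22:00.
- Report the same analyses with the 24-hour diary mean alongside, as a prespecified sensitivity analysis.
- Report the number and urgency of out-of-window voids separately, and state whether the waking questionnaire enters any ESM score.
- Carry the definition into section 6.2, which describes the diary score in the predictor analysis as end-of-day where section 6 uses the day-mean. The two need reconciling.
- State as a limitation that the diary scores urgency at voids and ESM at random moments. Matching the windows does not remove this.

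The cost is a few sentences and no new data, since void times are already recorded. The downside is that a few diary entries per day leave the main contrast, and the lack of night coverage in ESM must then be read from the 24-hour analysis.

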4.2.2 Tool development

To apply ESM as a symptom assessment method in this study, an application suitable for smartphones has been developed. This application runs the previously selected set of items, as described in section 5.2.1.1. 'PROM development'.

The application can be downloaded freely on the personal smartphone of each participating subject. Once the application is downloaded and activated, it will work both online and offline to ensure that no assessments will be missed when not connected to the Internet. In online situations the answers will be directly and automatically sent to the general database; when offline the answers will be temporary stored at the smartphone and will be sent to the database as soon as an Internet connection is available. Encryption of data to assure on patient's privacy is described in detail in section 9.1 'Handling and storage of data and documents'.

Questions in the application will be designed in a hierarchical order, *i.e.* if the patient has no symptoms at that particular moment, there is no rationale for assessing triggers and therefore these questions will be automatically set to a default of "no" or "none". Further, if patients find an auditory signal

disturbing during their daily activities, they will be able to choose a vibration signal instead.

- 4.2.3 Retrospective symptom assessment conventional questionnaires Apart from ESM, participants will be instructed to complete a SR-BD during last 3 consecutive days of filling out the ESM (see 'F2. ESM_sensationrelated bladder diary_Versie 1.0 (11.08.2017)'). The SR-BD has to be filled out after each micturition. This is a voiding diary where people fill out at what time they had to void, how high the voided volume was and how high the urgency and perception of bladder fullness was what they experienced. Furthermore they have to fill out if and how much urine loss they had. Furthermore, participants will be instructed to complete additional (singletime) retrospective questionnaires, at the end of the test period of 7 days:
 - Baseline questionnaire for demographic characteristics (see F1.
 'ESM_Algemene Vragenlijst_Versie 1.0 (11.08.2017)').
 - Sensation-related bladder diaries (see 'F2. ESM_sensation-related bladder diary_Versie 1.0 (11.08.2017)'). Besides urinary frequency and voided volume, these diaries also include the degree of urge and the perception of bladder fullness during each void. It has been recommended that evaluation of bladder sensations during daily activities is the most representative. ⁴⁸⁻⁵⁰ Sensation-related bladder diaries (SR-BDs) are a non-invasive tool that is used to evaluate these bladder sensations in daily life.
 - Overactive Bladder Questionnaire (OAB-q) (see F1. 'ESM_OABq_Versie1.0 (2016.10.17)'). 33-item questionnaire on LUTS and Health-related quality of life (HRQL) items.⁵¹
 - 3 Incontinence Questionnaire (3IQ) (see 'F1. ESM_3IQ_Versie 1.0 (11.08.2017)')⁵²
 - Female participants only :
 - International Consultation on Incontinence Modular Questionnaire – Female LUTS (see F1. 'ESM_ICIQFLUTS_Versie 1.0 (11.08.2017)').13-item questionnaire on lower urinary tract symptoms ^{53,54}.
 - Vragenlijst Werkgroep Bekkenbodem NVOG (see 'F1. ESM_VragenlijstNVOG_Versie 1.0 (11.08.2017)'). 47-short item questionnaire on pelvic symptoms.

- Male participants only:
 - International Consultation on Incontinence Modular Questionnaire – Male LUTS (see 'F1. ESM_ICIQMLUTS_Versie 1.0 (11.08.2017)').13-item questionnaire on lower urinary tract symptoms ^{53,54}.
 - International Prostate Symptom Score (see 'F1. ESM_IPSS_Versie 1.0 (11.08.2017)'). 7 item questionnaire on LUTS and 1 item questionnaire on Quality of Life⁵⁵.
 - International Index of Erectile Functions 5 (IIEF-5) (see 'F1. ESM_IIEF5_Versie 1.0 (11.08.2017). 5-item questionnaire to screen for erectile dysfunction. ⁵⁶
- Hospital Anxiety and Depression Scale (HADS) ((see 'F1. ESM_HADS_Versie 1.0 (11.08.2017)').⁵⁷
- Short Form-36 (SF-36) (see F1. ESM_SF36_Versie 1.0 (11.08.2017)'). Self-survey after general quality of life (not disease-specific)⁵⁸

Figure 2: Questionnaire timeline.

